10.3.2 Primary outcome analysis

The primary outcome will be presented as a proportion with a 95% Jeffreys credible interval with equaltail probabilities.

10.3.3 Secondary outcome analysis

Credible intervals for proportions:

(Such as "the proportion of eligible recipients who consent to take part in the study)
95% Jeffreys credible interval with equal-tail probabilities will be defined for the proportions of interest.

Tests of differences in proportions:

(Such as the difference in PGD rates between the two solutions of interest)

Difference between two proportions defined on independent samples will be assessed by means of exact fisher or score tests. 95% CI for the difference in proportions will be defined by inverting the score test. Logistic regressions may be considered to control for selected confounders. Penalised likelihood will be used in case of perfect separation of the binary outcome by a set of predictor levels.

Tests of independence between pairs of categorical variables:

(Such as the association between grade 3 PGD and treatment)

The independence of rows and columns of contingency table with fixed marginals will be assessed by means of Fisher's exact tests. Ordinal regressions may be considered to control for selected confounders. Partial proportional odds models will be considered if the proportional odd assumption is violated.

Test of equality of two independent means for continuous outcomes:

(Such as the equality of means of some echocardiographic parameter per treatment group)

Welch t-tests will be used to compare the means of two independent samples for continuous outcomes. Transformations (like log, box-cox) will be used in case of strong deviations to normality of the residuals within each group. Wilcoxon rank sum tests may be used as sensitivity analyses or when the comparison of medians (instead of means) is preferred. Linear regressions may be considered to control for selected confounders. Generalized Additive Models for Location, Scale and Shape models will be preferred in case of the presence of heteroscedasticity.

Test of equality of two independent means for bounded outcomes like proportions:

(Such as the association between left ventricular ejection fraction and treatment)

Welch t-tests will be used to compare the means of two independent samples for bounded outcomes like proportion. Transformations (like log, box-cox) will be used in case of strong deviations to normality of the residuals within each group. Wilcoxon rank sum tests may be used as sensitivity analyses. Beta regressions may be considered to control for selected confounders.

Analysis of survival outcomes:

(Such as the comparison of 30-day all-cause mortality by treatment group)

Survival rates through time of different groups will be compared by means of Kaplan-Meier plots and log rank tests will be used to compare the survival distributions per group. Cox regressions may be considered to control for selected confounders. The proportional hazard assumption will be assessed by means of Schoenfeld residual analysis.

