10 STATISTICS AND DATA ANALYSIS

10.1 Sample size calculation

This is a feasibility study, so formal sample size calculation is not required. However, 50 hearts will give a 95% confidence interval of 53%-79% assuming a primary outcome rate of 66%.

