10.2 Planned recruitment rate

A proportion of two-thirds for the primary outcome will be considered successful, as it would correspond to a yearly average of approximatively 80 patients being recruited in the main study, assuming a yearly number of available hearts of 120 (corresponding to the yearly observed number of adult DBD heart transplants in the UK during the last two years).

A power calculation for a superiority trial based on the development of primary graft dysfunction as the primary outcome showed that a sample size of 400 patients would allow detection of a 14% absolute risk reduction in PGD between the two solutions of interest (from 36% to 22%) corresponding to an odds ratio of 0.5 (or 17 cases of PGD prevented per year) with a probability (power) of 0.85 with a type I error of 0.05 when considering a two-sided test of difference in proportions. As approximately 120 adult DBD heart transplants are performed in the UK each year, we estimate that the larger trial will take 5 years to complete (i.e., $80 \times 5 = 400$).

For this feasibility trial to meet its recruitment target, we anticipate a recruitment rate of 80 patients per year, over a period of 6-12 months. 1 patient per site per month would result in a 9-month recruitment period.

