10.5 Adjusted analysis

F-CUSToS Protocol Version Number 2.0; Dated 30 January 2025

As outlined above, risk adjustment for baseline value of CPOi (at admission to ICU) will be used in the linear regression for difference in CPOi between admission to ICU and 6 hours post-transplant. All linear and logistic regression models will be adjusted for confounders of interest and presented alongside single comparison tests, such as Fisher's exact test without adjustment.

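### Penalised likelihood is tied to perfect separation, a trigger that would almost never act with 50 randomised hearts; Firth estimation for every adjusted logistic model would be a cheap improvement

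*Protocol*

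**What the plan says.** Section 10.3.3 compares binary outcomes such as PGD by Fisher's exact or a score test, with an interval for the difference in proportions from the inverted score test. It then adds that "Logistic regressions may be considered to control for selected confounders" and that "Penalised likelihood will be used in case of perfect separation of the binary outcome by a set of predictor levels". Section 10.5 says "All linear and logistic regression models will be adjusted for confounders of interest", with these models shown next to the unadjusted tests. Neither section names or counts the confounders.

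For survival outcomes, 10.3.3 plans Kaplan-Meier plots and log-rank tests and adds "Cox regressions may be considered to control for selected confounders". It states no fallback for a Cox model with very few deaths.

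**The concern.** Perfect separation is only the extreme end of sparse-data bias. Maximum likelihood estimates of a log odds ratio lie, on average, too far from zero when events are few, and they do so in samples where every estimate is finite. A rule that waits for separation leaves that bias alone and changes the estimator only in the rarest, most extreme samples.

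At stake is the adjusted PGD odds ratio, which would tend to look somewhat stronger than the truth and be noisier than it needs to be. For the Cox model the issue is whether an estimate exists: if all deaths fall in one arm, the ordinary hazard ratio for treatment is not finite. The protocol foresaw this kind of failure for binary outcomes but not for survival, where it is more likely.

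**Working it through.** **The plan's own figure.** Section 10.2 gives 400 patients for PGD of 36% against 22%, "with a probability (power) of 0.85 with a type I error of 0.05 when considering a two-sided test of difference in proportions". The usual formula is n per arm = [1.96·√(2·0.29·0.71) + 1.036·√(0.36·0.64 + 0.22·0.78)]² / 0.14², which gives 188 per arm, or 376. With the continuity correction it is 202 per arm, or 404, which matches 400. The odds ratio is (0.22/0.78)/(0.36/0.64) = 0.501, so the log odds ratio is −0.690.

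**Events in this study.** With 25 hearts per arm: 25 × 0.36 + 25 × 0.22 = 14.5 PGD events. This takes 50 as the number randomised, as the recruitment text in 10.2 suggests: "1 patient per site per month would result in a 9-month recruitment period" (6 sites × 9 months = 54). Section 10.1 points the other way: "50 hearts will give a 95% confidence interval of 53%-79% assuming a primary outcome rate of 66" per cent. There 50 is the denominator of the two-thirds outcome: 0.66 ± 1.96·√(0.66·0.34/50) = 0.53 to 0.79. On that reading about 33 are randomised, with 33 × 0.29 ≈ 9.6 events.

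**Exact check without covariates.** Let i and j be the PGD counts in the two arms, binomial with n = 25 and rates 0.36 and 0.22. Averaging ln[j/(25−j)] − ln[i/(25−i)] over all samples with finite estimates gives −0.736 against the true −0.690, a bias of 6.7%. Separation has probability 0.2%. Adding 0.5 to each cell gives −0.692, a bias of 0.2%.

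**With covariates.** Model: logit P(PGD) = α + β·treatment + γ·(x₁ + … + x_k), with β = −0.690, 29% events overall, 1:1 allocation and independent standard normal covariates. Both k and γ are assumptions. There were 4,000 trials per setting, with a Monte Carlo error of about 2 percentage points. Maximum likelihood (ML) excludes separated fits.

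| k | γ | ML bias | ML SD | Separated | Firth bias | Firth SD |
|---|---|---|---|---|---|---|
| 2 | 0.4 | 11.5% | 0.79 | 0.3% | −0.3% | 0.70 |
| 3 | 0 | 15.9% | 0.79 | 0.2% | 1.0% | 0.68 |
| 3 | 0.4 | 17.6% | 0.85 | 0.2% | 1.2% | 0.72 |
| 5 | 0 | 22.7% | 0.88 | 0.3% | 1.4% | 0.71 |
| 5 | 0.4 | 31.0% | 0.98 | 0.7% | 4.6% | 0.78 |
| 6 | 0.4 | 33.7% | 1.03 | 1.9% | 4.7% | 0.80 |

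Other runs of the same design gave 10-14% for two covariates, 15-18% for three and 26-29% for five.

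- Odds ratio scale: with k = 3 and γ = 0.4 the mean estimate is exp(−0.690 × 1.176) = 0.44, and with k = 5 it is exp(−0.690 × 1.310) = 0.40, against 0.50.
- Bias against noise: with k = 2, 0.115 × 0.690 = 0.079, and 0.079/0.79 = 0.10 SD. With k = 5, 0.310 × 0.690 = 0.214, and 0.214/0.98 = 0.22 SD.
- Root mean square error, k = 3 and γ = 0.4: ML √(0.85² + 0.121²) = 0.86; Firth √(0.72² + 0.008²) = 0.72.
- About 33 randomised: ML bias is 14-36% for two to five covariates, separation 2-10%, and Firth bias −1% to 8%.

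**Cox model.** With mortality m and n per arm, let q = (1 − m)ⁿ. Exactly one arm has no deaths with probability 2q(1 − q).

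- m = 11.2% (the complement of the 88.8% survival alarm limit in section 7.10), n = 25: q = 0.051, giving 10%.
- m = 8% (assumed), n = 25: q = 0.124, giving 22%.
- m = 5% (assumed), n = 25: q = 0.277, giving 40%.
- n = 16: 25%, 39% and 49% in the same order.

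**The case against.** The case for leaving the text alone has real substance.

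- *The planned comparisons are untouched.* PGD is compared by Fisher or score test with a score interval, and mortality by log-rank. Adjusted models appear alongside these. This stands, and it is the main reason the point is small.
- *The bias is modest.* It is about a tenth to a fifth of one standard deviation, and median bias is smaller than mean bias (about 5-23% for two to five covariates). With 1:1 allocation it vanishes by symmetry at an odds ratio of 1, so it does not create an effect from nothing. This stands.
- *The percentages are not properties of the protocol.* They depend on how many covariates are used, on 50 randomised hearts and on a true odds ratio of 0.5. This stands, so each figure must carry its condition.
- *The protocol does not forbid penalisation elsewhere, and the analysis plan, not seen here, may settle it.* That is fair. Still, the protocol writes down one trigger, and on the natural reading everything else is ordinary maximum likelihood.
- *Sections 10.3.3 and 10.5 can be reconciled:* regressions are optional, and those fitted are adjusted. Accepted; no contradiction is claimed.

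A reader might also infer that an inflated adjusted odds ratio would distort the planning of the main trial. The documents do not support that. Sections 2 and 10.2 already fix the main trial's PGD rates and size, and section 3.3.1 bases progression on the feasibility proportion. Nor is the Cox model bound to fail: it is optional, no expected mortality is stated, and 11.2% reflects an alarm limit.

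**Conclusion.** The point holds as a choice of method that can be bettered at almost no cost. With 50 randomised hearts, a true odds ratio of 0.5 and two to five covariates, the rule as written leaves an inflation of roughly 10-31% in the adjusted PGD log odds ratio. The stated safeguard would act in about 2% of trials or fewer. If only about 33 are randomised, the inflation is larger and separation somewhat more common. In the settings simulated, Firth estimation reduces both bias and variance, so accuracy gives no reason to prefer the present rule.

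The consequence is limited to a secondary, adjusted estimate in a feasibility study. It does not touch the primary outcome, the unadjusted PGD comparison or the log-rank test. The gap for the Cox model is real but conditional on that model being fitted.

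**What to change.** In section 10.3.3, replace the sentence on penalised likelihood with:

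> Adjusted logistic models will use Firth penalised likelihood with penalised profile-likelihood intervals, whether or not separation occurs; if a Cox model is fitted, the same penalty will be used.

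No minimum event count needs to be added. A cutoff of ten events, for example, would rule out a Cox mortality model in at least 95% of trials at mortality rates of 5% to 11.2%. The penalty gives a finite hazard ratio when one arm has no deaths. It cannot help when there are none at all (0.277² = 7.7% of trials at an assumed 5% mortality with 25 per arm), and the report should then say that no hazard ratio was estimated.

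The cost is one sentence and a standard software option. The downside is slight shrinkage and an estimator less familiar to some readers. Because the unadjusted tests are still shown alongside, nothing already planned is lost.

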- iii. Body surface area calculated using the DuBois and DuBois formula: Body Surface Area= 0.007184 x (Height(m) $^{0.725}$) x (Weight(kg) $^{0.425}$).
- iv. Mean Arterial Pressure (mmHg) on invasive intra-arterial blood-pressure monitoring at the time of Swan-Ganz measurements.
- v. Central Venous Pressure (mmHg) on invasive central venous pressure monitoring at the time of Swan-Ganz measurements.

As this is an exploratory outcome measure, with the intent to assess its utility based on real-world data, this will be assessed based on the above data being recorded on the intensive care electronic health record system. The measurements will be taken and recorded by the healthcare professional(s) looking after the participant. Where the outcome assessor transferring this data from the healthcare record to the trial database cannot find a measurement within the stipulated timeframe, this will be treated as missing data.

PGD will be determined based on the ISHLT consensus statement 2014 (2) and graded accordingly. PGD is defined as occurring within 24 hours, therefore all measurements included below must be taken within the first 24 hours after admission to ICU post-transplant procedure. Its definition requires the following variables to be recorded on the database:

F-CUSToS Protocol

Version Number 2.0; Dated 30 January 2025

- Ejection fraction on echocardiogram; where multiple measurements are taken the lowest estimate of ejection fraction recorded will be inputted to the database.
- ii. Haemodynamic variables taken at the time of a Swan Ganz measurement*:
 - (i) Central Venous Pressure (mmHg)
 - (ii) Pulmonary capillary wedge pressure (mmHg)
 - (iii)Cardiac Output (L/min)
 - (iv) Cardiac Index (L/min/m2)
 - (v) Mean Arterial Pressure (mmHg)
 - (vi)Transpulmonary gradient (mmHg)
 - (vii) Pulmonary artery systolic pressure (mmHg)
- iii. Vasoactive Inotrope Score (VIS), where VIS = dopamine [μ g kg⁻¹ min⁻¹] + dobutamine [μ g kg⁻¹min⁻¹] + 100×adrenaline [μ g kg⁻¹ min⁻¹] + 50×levosimendan [μ g kg⁻¹ min⁻¹] + 10×milrinone [μ g kg⁻¹ min⁻¹] + 10 000×vasopressin [units kg⁻¹ min⁻¹] + 100×noradrenaline dose [μ g kg⁻¹ min⁻¹].
- iv. Presence/absence of an intra-aortic balloon pump (IABP).
- v. Presence/absence of mechanical circulatory support (ECMO/LVAD/RVAD/BiVAD).

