*Where multiple Swan Ganz measurements are taken within the first 24 hours after transplant, the set of variables taken at the same time as the highest inotrope score should be uploaded to the CRF. Where there are multiple Swan Ganz measurements with the same inotrope score the set of variables with the lowest cardiac output should be uploaded to the CRF.

The following echocardiographic parameters from trans-oesophageal echo immediately after transplant implantation will be recorded in the initial outcome data collection CRF:

- i. Left Ventricular ejection fraction (% estimated by Simpson's biplane method)
- ii. Left ventricular maximal posterior wall thickness (in mm)
- iii. Maximal septal wall thickness (in mm)
- iv. Left ventricular function (good, moderate, poor or very poor)
- v. Right ventricular function (good, moderate, poor or very poor)
- vi. The presence/absence of any regional wall motion abnormalities as determined by the TOE operator

30-day outcome data collection: The delegated individual(s) in the recipient centre should upload the 30-day mortality, postoperative complication, length of initial ICU stay, and length of initial hospital stay data, on the 31st day after the transplant procedure. This should be conducted in accordance with the blinding instructions laid out in section 7.4 of this Protocol. The variables will be entered into the CRF as follows:

- i. 30-day mortality: alive/dead
- ii. Post-operative complications:
 - (i) Dysrhythmias (any within 30 days):
 - 1. Atrial fibrillation yes/no
 - 2. Ventricular tachycardia yes/no
 - 3. Ventricular fibrillation yes/no
 - 4. Other rhythm abnormality yes/no (specify)
 - (ii) Myocardial Infarction within 30 days (defined according to ESC definitions of myocardial infarction post-cardiac surgery): yes/no

- (iii)Stroke within 30 days (defined by radiological evidence of ischaemia/haemorrhage and clinical symptoms of stroke): yes/no
- (iv)Transplant rejection within 30 days (defined by the clinical team and confirmed on histopathology of biopsy material or post-mortem): yes/no
- (v) Infection within 30 days (from any source requiring antibiotic therapy): yes/no (specify suspected source)
- (vi) Venous thromboembolism within 30 days (defined by radiological evidence and need for treatment): yes/no (specify PE/DVT)
- (vii) 30-day re-admission to any UK hospital: yes/no
- (viii)Hyponatraemia within 24 hours of transplant (Na<125mEq/L on serum sample, not blood gas analysis): yes/no

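### The only firm unadjusted test for categorical outcomes ignores category order, so it wastes information on the four-level LV and RV function grades (minor)

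*Protocol*

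**What the plan says.** Section 10.3.3 sets out methods by class of outcome. For pairs of categorical variables it states: "The independence of rows and columns of contingency table with fixed marginals will be assessed by means of Fisher's exact tests". The example given is "Such as the association between grade 3 PGD and treatment".

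Two further sentences in that paragraph bring in models that use order: "Ordinal regressions may be considered to control for selected confounders" and "Partial proportional odds models will be considered if the proportional odd assumption is violated". Section 10.5 adds that adjusted linear and logistic models will be "presented alongside single comparison tests, such as Fisher's exact test without adjustment".

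The outcomes with ordered categories are defined in section 7.7:
- "Left ventricular function (good, moderate, poor or very poor"
- "Right ventricular function (good, moderate, poor or very poor"
- "PGD will be determined based on the ISHLT consensus statement 2014 (2) and graded accordingly"

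Section 3.3.2 lists LV function and RV function as secondary endpoints (vi.d and vi.e). It lists PGD as whether PGD develops (v), not as a grade.

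**The concern.** The Fisher test of a 2 x 4 table asks whether the two arms differ in any way at all. Swap the labels good and very poor in both arms and the p-value does not change. The test therefore spreads its sensitivity over every pattern of difference, and a small p-value does not say which solution did better.

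The ordinal models do not fill the gap. They are optional and tied to confounder control, and section 10.5's firm wording covers linear and logistic models only. As written, no unadjusted comparison that uses order is specified for the echo grades. Yet the proportional-odds wording shows that ordered outcomes were expected under this heading, and section 10.3.3 already allows the Wilcoxon rank-sum test for continuous and bounded outcomes.

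At stake are some power and a usable effect estimate for two secondary endpoints.

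**Working it through.** **Inputs from the protocol.** 50 hearts (section 10.1), allocated 1:1 (section 4), so 25 per arm. PGD 36% against 22%, odds ratio 0.5, two-sided alpha 0.05, power 0.85 with 400 patients (section 10.2).

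**The plan's own figure.** Odds ratio = (0.22/0.78) / (0.36/0.64) = 0.282 / 0.5625 = 0.501. At 200 per arm the power is 0.851 with the exact Fisher 2 x 2 test and 0.848 with a continuity-corrected test of proportions. The plan's 0.85 reproduces. The protocol gives no power figure for any ordered outcome.

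**Assumptions not in the protocol.**
- Grade distributions for LV and RV function: 50/30/15/5% and 40/30/20/10%, with an even 25/25/25/25% split as an outer case.
- A common odds ratio of 0.5 across the grades, borrowed from the PGD effect.
- All 50 hearts randomised and graded.

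**Second arm.** For each cut k, let P(k) be the probability of a grade worse than k. Then odds2(k) = 0.5 x P(k)/(1 - P(k)). For 40/30/20/10%:
- Worse than good: 0.60, odds 1.5, halved 0.75, probability 0.429
- Poor or worse: 0.30, odds 0.429, halved 0.214, probability 0.176
- Very poor: 0.10, odds 0.111, halved 0.056, probability 0.053

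Differencing gives 57.1/25.2/12.4/5.3%. The same steps turn 50/30/15/5% into 66.7/22.2/8.5/2.6%.

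**Power.** All 2 x 4 tables at 25 per arm were enumerated. The exact Fisher r x c test was compared with the exact Wilcoxon test on mid-ranks, two-sided at 0.05.

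| First-arm split | Odds ratio | Fisher | Exact Wilcoxon | Gap (points) |
|---|---|---|---|---|
| 50/30/15/5% | 1 (type I error) | 4.8% | 4.6% | – |
| 40/30/20/10% | 1 (type I error) | 4.9% | 4.7% | – |
| 50/30/15/5% | 0.5 | 15.8% | 21.8% | 6 |
| 40/30/20/10% | 0.5 | 16.4% | 24.2% | 8 |
| 25/25/25/25% | 0.5 | 17.1% | 26.1% | 9 |
| 50/30/15/5% | 0.25 | 48.1% | 60.8% | 13 |
| 40/30/20/10% | 0.25 | 52.3% | 67.8% | 15.5 |

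**PGD grade, if compared over four levels.** The 36% total is the plan's; the number of levels and the split are assumptions. At odds ratio 0.5, a 64/12/12/12% split gives 12.6% against 18.2%, and 64/4/20/12% gives 13.6% against 17.8%, gaps of about 4 to 6 points.

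**Effects that do not follow the order.** With 64/12/12/12% against 64/20/14/2% (same PGD incidence, fewer cases in the worst grade), Fisher has 16.5% power and Wilcoxon 5.6%. With 40/30/20/10% against 30/55/14/1%, Fisher has 35.1% and Wilcoxon 5.8%.

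**The case against.** Fisher's test is valid here and its type I error is controlled. The study has no formal sample size and no power target for secondary outcomes, and neither test exceeds about 26% power at an odds ratio of 0.5. Section 10.3.3 works by class of outcome and assigns no test by name to LV or RV function; such detail may sit in a separate statistical analysis plan. The Wilcoxon advantage also depends on a shift along the scale. The last comparison above shows it can lose badly, and the plan's interest in grade 3 PGD makes a change confined to the worst grade a plausible pattern. All of this stands and keeps the point small. It does not remove it: the protocol states a firm choice for categorical tables, and that choice suits ordered grades poorly.

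A reader might infer three stronger things.
- **That PGD grade is a third ordered endpoint analysed this way.** The listed endpoint is whether PGD develops, section 10.3.3 treats PGD rates as proportions, and grade 3 PGD reads naturally as yes/no. A 2 x 2 table has no order to lose.
- **That the loss reaches 15 points or more.** Under the two main splits this needs an odds ratio near 0.25, which the protocol does not state.
- **That the loss carries over to the 400-patient trial,** since section 4 says this design replicates it. That trial is sized on a two-sided comparison of PGD proportions. A full-grade Fisher test is not its planned primary analysis, so the documents do not support the inference.

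**Conclusion.** The point holds for LV and RV function, and for PGD grade only if it is compared across all its grades. The one firm unadjusted test discards the order of the categories and yields no direction of effect. The cost is about 6 to 8 points of power at 25 per arm (about 16% against 22% to 24%), with 9 points in the even-split case. These figures rest on assumed grade distributions and on carrying the plan's PGD odds ratio over to the echo grades as a common shift. Larger gaps need larger assumed effects. Severity is minor: these are secondary outcomes of a feasibility study, and power is low with either test. The more useful gain is an estimate with a direction and an interval.

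**What to change.** In section 10.3.3, keep Fisher's exact test for binary and nominal tables. For LV function, RV function and any full-scale comparison of PGD grade, make the unadjusted comparison either the exact Wilcoxon rank-sum test with mid-ranks or an unadjusted proportional-odds model. Report the common odds ratio with its 95% CI, and tabulate the proportion in each grade by arm. State whether grade 3 PGD is a yes/no comparison, and amend the Fisher example in section 10.5 to match.

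The cost is a few sentences and no new data. The downside is lost power when the effect does not follow the order of the grades. The table by arm lets a reader see such a pattern, and the partial proportional-odds provision already in the section covers a failed common-shift assumption.
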